#### 4.4.4. Home follow-up visits (Visit 03 through Visit 08, 1-6 days post vaccination $\pm$ 0 day)

A field worker will visit the participant at home to:

- Inquire about the child's health (any illnesses or medications taken or visits to a healthcare facility).
- Inquire about any reactions using a standard questionnaire to record the local and systemic reactogenicity after vaccination.

- Remind the parents that they will need to bring their child to the FSC on the 7th day (+ 3 days) following vaccination for a blood draw and to check on the welfare of the child.
- Remind the parents to seek medical care as appropriate and inform the investigator as soon as possible in the event of an adverse reaction or SAE. If the child visits a health care provider, the parents should be sure to inform him/her of the child's participation in the study and present the provider with contact information for the investigator as indicated on the study identification card.
- Complete the appropriate section(s) of the CRF.

#### **4.4.5. Clinic follow-up visit (Visit 09, 7 days post vaccination +3 days)**

When the parent or legal guardian brings their child to the FSC/ Mirpur study clinic on the scheduled day for follow-up, the study team will:

- Inquire about the child's health (any illnesses or medications taken or visits to a healthcare facility).
- Inquire about any reactions using a standard questionnaire to record the local and systemic reactogenicity after vaccination.
- Collect 2 ml of blood from participants with aseptic technique to detect anti-JE serum neutralizing antibody and anti-JE IgM with PRNT-50 and ELISA, respectively
- Inform parents that they will need to bring their child to the FSC at Matlab or Mirpur study clinic in approximately 28 days ( $\pm 7$  days) in order to check on the welfare of the child and assess the occurrence of any adverse events.
- Remind parents to seek medical care as appropriate and inform the investigator as soon as possible in the event of an adverse event or SAE. If the child visits a health care provider, the parents should be sure to inform him/her of the child's participation in the study and present the provider with contact information for the investigator as indicated on the study identification card.
- Complete the appropriate section(s) of the CRF.

#### **4.4.6. Clinic follow-up visit (Visit 10, 28 days post vaccination $\pm 7$ days)**

A final study visit will be conducted 28 days after booster vaccination. The study team will:

- Inquire about the child's health (any illnesses or medications taken or visits to a healthcare facility).
- Inquire about any adverse events.
- Collect 2 ml of blood from participants with aseptic technique to detect anti-JE serum neutralizing antibody with the PRNT-50.
- Complete the appropriate section(s) of the CRF.
- Exit the participant from the study.

#### **4.4.7. Booster Vaccine**

Although studies have shown that the JE live attenuated SA 14-14-2 vaccine (CD-JEV) produces long lasting immunity, China and India currently give a boosting dose at least one year after the primary vaccination. In a recent 2015 position paper regarding JE vaccines (Weekly Epidemiological record Feb 27, 2015; <http://www.who.int/wer>), WHO stated that "long-term immunogenicity studies would inform optimal dosing schedules for long-term protection, which may vary by location (based on natural boosting or other factors)". As an important research need for all of the newer JE vaccines, the proposed study will provide data for guiding policy decisions with regard to the booster dose for CD-JEV, as it would be impossible for routine immunization programs to select only seronegative children for boosting. Including participants seroprotected 3 years post

vaccination at the 4 year time point of booster dose is important to understand the kinetics of the antibody response in children with existing titers and provide information for optimal schedules.

## **4.5. Laboratory evaluations**

### **4.5.1. Clinical laboratory evaluations**

There will be no clinical (safety) laboratory evaluations in this study. Laboratory assays specified in Section 4.5.2 are for research purposes only and are not be used for clinical diagnosis.

### **4.5.2. Serum assays**

#### **4.5.2.1. Anti-JE neutralizing antibody titer**

Serum anti-JE neutralizing antibody titers will be measured using PRNT at the United States Army Medical Directorate, Armed Forces Research Institute of Medical Sciences in Bangkok, Thailand. The reported titer will be the PRNT-50 which is the highest serum dilution that is still capable of reducing the number of virus plaques in cell culture by 50% compared to virus growth in cell culture without any added serum. Seroprotection will be defined as a PRNT-50 titer of  $\geq 1:10$ .

#### **4.5.2.2. Anti-JE IgM**

Anti-JE IgM will be measured on specimens collected prior to the booster dose and 7 days following the booster dose using ELISA at United States Army Medical Directorate, Armed Forces Research Institute of Medical Sciences in Bangkok, Thailand. Seropositivity will be defined per the manufacturer's kit instructions.

### **4.5.3. Specimen preparation, handling, and shipping**

#### **4.5.3.1. Specimen collection**

Blood draws of 2 ml will be collected during study visits. The identity of the child will be verified immediately prior to the blood draw using the child's study participant number. The study participant number and date of collection of the specimen will be recorded on all labels to be used in the study. One label will be affixed onto the vacutainer tube immediately prior to the blood sample drawing.

After collection, blood samples must clot for 60 minutes to 2 hours at room temperature. Samples will then be kept in a cold box for transportation until processed in the site laboratory. All samples will be centrifuged on the same day of collection.

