## 4. RESEARCH DESIGN AND METHODS

The proposed study is a phase 4 open-label trial enrolling up to 818 Bangladeshi children who had previously participated in JEV05, a PATH-supported clinical study conducted from May to December 2012 during which 10- to 12-month-old infants were given a single dose of CD-JEV. Eligible JEV05 participants who still live in the

area will be identified using the local health and demographic surveillance system (HDSS) and asked to participate. Children will be divided into two groups based on whether they received vaccine from the old or new facility in JEV05:

- Group A (up to 655 eligible): children randomized to Groups 2-4 (new facility) in JEV05.
- Group B (up to 163 eligible): children randomized to Group 1 (old facility) in JEV05.

An overview of the study activities is provided in Table 3. A 2 ml blood sample will be collected from all participants three and four years after initial vaccination. The sera will be tested using PRNT; JE neutralizing antibody titers  $\geq 1:10$  will be considered seroprotective.

After the blood draw at Visit 02 occurring in May to December 2016, four years after their initial vaccination, both groups will receive a single subcutaneous booster dose of CD-JEV. Additional serum samples will be collected on Day 7 and Day 28 following the booster dose for measurement of serum anti-JE neutralizing antibody titers.

Following the booster dose, children will be monitored for immediate reactions during the first 30 minutes, solicited injection site and systemic adverse reactions for 7 days, unsolicited adverse events and serious adverse events for 28 days. All safety events will be identified or observed by study staff during home visits, clinic visits, and/or reported by a parent or legal guardian. Solicited and systemic adverse reactions will be assessed through home visits 1 through 6 days following vaccination, and a fixed site clinic (FSC) visit on Day 7 following vaccination. Information regarding unsolicited AEs occurring in the 28 days following vaccination will be collected and recorded on a standard questionnaire during clinic visits. Events will be graded for severity and assessed for relatedness to vaccination by the investigator.

The study will be open-label; no placebo control will be employed and safety assessments will be unblinded.

[figure not shown]

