#### **4.5.3.2. Specimen preparation, handling, and storage**

After centrifugation, the serum will be aliquoted. To insure that samples are not mixed or inaccurately labeled, the child's study participant number, date of blood collection, number of aliquots obtained, and the date and time of aliquoting will be specified on the sample identification log. A label will be affixed onto each of the aliquots. Comments may be made on the quality of samples (e.g., hemolyzed, contaminated).

All serum aliquots will be kept in the -20°C freezer at the local study site. Study staff will monitor and record temperature on the appropriate form during the entire trial. One serum aliquot will be shipped to United States Army Medical Directorate, Armed Forces Research Institute of Medical Sciences in Bangkok, Thailand. A second aliquot will be retained at the site as back up and shipped to a long term storage facility determined by the Sponsor at the completion of the study. All unused serum specimens will be stored at their assigned location for 5 years following study completion. Samples will be destroyed after 5 years. Only authorized study staff should have access to the samples. Samples will not be used for unrelated, future studies without an institutional review board (IRB) approved amendment to the protocol.

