#### **4.5.3.3. Specimen shipment**

Specimens will be shipped according to the International Air Transport Association regulations after each study year.

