### **7.6.2. Data capture methods**

Clinical data and laboratory data will be recorded on CRFs. All children will be assigned a unique study participant number at study enrollment; this study participant number will be included on all forms and in the computer database and will serve to link study data to specific individuals. Data forms will be verified for accuracy, linked by study participant number, and managed using database management software (yet to be determined).

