**Table 4. Allowable Schedule**

Study Visit	Should occur	May occur
Visit 01	Three years after initial vaccination	Three years $\pm$ 3 months after initial vaccination
Visit 02	Day 365	One year $\pm$ 28 days after Visit 01
Visit 03	Day 366	1 day after booster vaccination
Visit 04	Day 367	2 days after booster vaccination
Visit 05	Day 368	3 days after booster vaccination
Visit 06	Day 369	4 days after booster vaccination
Visit 07	Day 370	5 days after booster vaccination

Study Visit	Should occur	May occur
Visit 08	Day 371	6 days after booster vaccination
Visit 09	Day 372	7 to 10 days after booster vaccination
Visit 10	Day 393	21 to 35 days after booster vaccination

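### Specimen labels carry participant number and collection date, and neither document masks the laboratory, so a child's pre-booster and post-booster sera can be told apart when the plaque assay is read

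*Protocol*

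**What the plan says.** The labelling rule in Protocol 4.5.3.1 has no exceptions: "The study participant number and date of collection of the specimen will be recorded on all labels to be used in the study". Section 4.5.3.2 carries it forward to the aliquots ("A label will be affixed onto each of the aliquots") and then sends one away: "One serum aliquot will be shipped to United States Army Medical Directorate, Armed Forces Research Institute of Medical Sciences in Bangkok, Thailand". No step replaces the number or the date with a code.

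Section 7.6.2 makes the number personal to the child: "All children will be assigned a unique study participant number at study enrollment". Section 4.5.3.3 sets the timing: "Specimens will be shipped according to the International Air Transport Association regulations after each study year". On the natural reading, the Year 4 pre-booster, Day 7 and Day 28 sera travel together, after the Year 3 sera.

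On blinding, Protocol section 4 says only: "The study will be open-label; no placebo control will be employed and safety assessments will be unblinded". SAP 2.2 has the same scope. Neither document mentions laboratory masking, coded samples or a random testing order.

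The laboratory reads PRNT-50 on all sera (Protocol 4.5.2.1). It also runs the IgM ELISA, on pre-booster and Day 7 sera only (Protocol 4.5.2.2).

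**The concern.** The booster results are within-child comparisons with no unboosted control. Protocol 6.1 and SAP 6.2 compare Day 7 and Day 28 GMTs with the Year 4 pre-booster GMT by paired t-test. SAP 6.1 defines seroconversion by crossing 1:10 or by a four-fold rise. SAP 6.3.2 uses the Day 7 four-fold rise to separate primed from unprimed children. All of these depend on PRNT-50 titres.

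If knowing the time point influenced a reading, the expected direction would be lower before the booster and higher after it. With no control arm, such an error would not cancel, and the planned confidence intervals cover sampling error only. The results are meant to guide booster policy (Protocol 4.4.7), so this route to bias should be closed while that is still possible. Masking cannot be restored after the sera have been read.

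**Working it through.** **1. Can number plus date order a child's sera?** The inputs are the visit windows, counted in days from the booster at Visit 02.

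| Serum | Protocol Table 4 | SAP Table 1 |
|---|---|---|
| Visit 02, pre-booster | 0 | 0 |
| Visit 09 | 7 to 10 | 4 to 10 (printed as ±3) |
| Visit 10 | 21 to 35 | 21 to 35 |

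Smallest gap from Visit 02 to Visit 09: 7 − 0 = 7 days (4 under the SAP window). Smallest gap from Visit 09 to Visit 10: 21 − 10 = 11 days. The windows do not overlap, so the order is unambiguous.

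The date alone would not be enough. Protocol section 4 says: "After the blood draw at Visit 02 occurring in May to December 2016, four years after their initial vaccination, both groups will receive a single" booster dose. From 1 May to 31 December is 244 days, so a given date could belong to any of the three visits. The number and the date are needed together, and the label carries both.

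**2. How much could it matter?** The plan gives no figure for reading error, so this is an illustration under stated assumptions.

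*Spread of titres.* From the 95% CIs in Protocol Table 2, SD = [log10(upper/lower) ÷ 2 ÷ t] × √n.
- Group 1: log10(100.4/59.6) ÷ 2 = 0.1132; 0.1132 ÷ 1.976 × √146 = 0.69.
- Groups 2 to 4: log10(63.8/49.5) ÷ 2 = 0.0551; 0.0551 ÷ 1.964 × √581 = 0.68.

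I assume lognormal titres with SD 0.69, and that this Day 28 spread also holds at the later time points.

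*Sera able to cross 1:10.* One two-fold step is 0.301 ÷ 0.69 = 0.436 SD. With seroprotection rate p, the cut-off lies at c = Φ⁻¹(1 − p). A downward error can move only sera just above the cut-off; an upward error can move only sera just below it.
- Share just above = Φ(c + 0.436) − (1 − p).
- Share just below = (1 − p) − Φ(c − 0.436).

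At p = 60%, c = −0.253. Above: Φ(0.183) − 0.400 = 0.173. Below: 0.400 − Φ(−0.690) = 0.155.

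At p = 80%, c = −0.842. Above: Φ(−0.405) − 0.200 = 0.143. Below: 0.200 − Φ(−1.278) = 0.099.

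*Shift in the rate* = fraction misread × share able to cross, in percentage points:

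| Fraction misread (assumed) | 60%, down | 60%, up | 80%, down | 80%, up |
|---|---|---|---|---|
| 1% | 0.17 | 0.15 | 0.14 | 0.10 |
| 5% | 0.86 | 0.77 | 0.71 | 0.50 |
| 10% | 1.73 | 1.55 | 1.43 | 0.99 |

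*Yardstick.* SAP Table 2 gives full widths of 95% intervals. The Wilson formula reproduces them to within about 0.001 (Group A, 10% attrition, 50% rate: 0.0804 against the printed 0.080). For rates of 50% to 80%, the Group A half-width runs from 3.2 points (n = 590, 80%) to 4.9 points (n = 393, 50%).

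**The case against.** The strongest reply is that opportunity is not bias. PRNT-50 is a 50% reduction against a no-serum control. The documents describe no reader discretion, and they do not say what the person counting plaques sees. Laboratory practice is left to SOPs, the study is descriptive, and no success threshold depends on the result. Most of this stands, and it limits the conclusion to a preventable weakness. It does not remove the point: the rule covers all labels, and an SOP outside these documents cannot be assumed to override it.

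A reader might also infer more than the documents support:

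- **That every immunogenicity endpoint is affected.** The exploratory IgM endpoint is an ELISA.
- **That the Group A versus Group B comparison is exposed.** Nothing shows that the label reveals the JEV05 group; the number is assigned at enrolment into this study.
- **That a Year 3 to Year 4 decline could be manufactured through the label.** Year 3 sera are all pre-booster. Yearly shipment, and the separate Year 3 interim analysis in SAP 3.7, show the study year whatever the label says.
- **That the plaque reading is the only step that could be masked.** The documents do not establish this. Masking to JEV05 group, for example, might have been possible for safety assessors or the statistician.
- **That about a third of sera are at risk.** At 60%, the share within one step on both sides is 0.173 + 0.155 = 33%, and 5% of that would be 1.6 points. A one-directional error can use only one side. Equal errors on both sides nearly cancel (0.77 − 0.86 = −0.09 points).

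**Conclusion.** The point holds as a design weakness. As written, the labels let the laboratory identify which of a child's Year 4 sera came before the booster and which came after, and nothing in either document prevents it. What is exposed is the set of PRNT-based pre/post-booster results.

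The documents give no evidence that bias occurs and no basis for its size. Under the stated model, a 5% one-directional misreading moves a seroprotection rate by 0.8 to 0.9 points at 60% and by 0.5 to 0.7 points at 80%. That is well inside the Group A half-width. The 5% is an assumption without a source, the shift scales in proportion to it, and the effect on the four-fold criterion is not quantified. The change is worth making because it is cheap and must come before testing, not because a large error has been shown.

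**What to change.** Before the Year 4 sera are tested:

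- Amend 4.5.3.1 and 4.5.3.2 so that shipped aliquots carry a random accession code, without participant number or date. Data management keeps the key until results are locked.
- Test a child's three Year 4 sera in the same run, in random order, from run lists prepared by data management.
- Release the list of sera for IgM testing only after the PRNT titres are locked. A list covering only pre-booster and Day 7 sera would otherwise single out the Day 28 sera.
- State in 4.5.2 that the laboratory is masked to time point. If a laboratory SOP already codes the samples, cite it there and correct the wording on labels.

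This does not hide Year 3 versus Year 4 while sera are shipped and tested by study year.

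The cost is relabelling and one more linkage step to quality-control. The upper limit is 818 × 3 = 2,454 Year 4 aliquots. With the 10% to 40% attrition assumed in SAP 2.3 and no later losses, it is about 1,470 to 2,210 (2,454 × 0.6 to 2,454 × 0.9). No extra blood or assays are needed. The site log and the retained back-up aliquot keep number and date for identity checks.

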#### **4.5.3.2. Specimen preparation, handling, and storage**

After centrifugation, the serum will be aliquoted. To insure that samples are not mixed or inaccurately labeled, the child's study participant number, date of blood collection, number of aliquots obtained, and the date and time of aliquoting will be specified on the sample identification log. A label will be affixed onto each of the aliquots. Comments may be made on the quality of samples (e.g., hemolyzed, contaminated).

All serum aliquots will be kept in the -20°C freezer at the local study site. Study staff will monitor and record temperature on the appropriate form during the entire trial. One serum aliquot will be shipped to United States Army Medical Directorate, Armed Forces Research Institute of Medical Sciences in Bangkok, Thailand. A second aliquot will be retained at the site as back up and shipped to a long term storage facility determined by the Sponsor at the completion of the study. All unused serum specimens will be stored at their assigned location for 5 years following study completion. Samples will be destroyed after 5 years. Only authorized study staff should have access to the samples. Samples will not be used for unrelated, future studies without an institutional review board (IRB) approved amendment to the protocol.

#### **4.5.3.3. Specimen shipment**

Specimens will be shipped according to the International Air Transport Association regulations after each study year.

### **5. SAMPLE SIZE CALCULATION AND OUTCOME (PRIMARY AND SECONDARY) VARIABLE(S)**

No sample size will be calculated for this study. However, up to 818 participants (up to 655 in Group A and up to 163 in Group B) who participated in JEV05 are expected to be enrolled in this study to evaluate the primary and secondary objectives.

#### **5.1. Serology variables**

Seroprotection for JE in this study is defined as percentage of participants with JE antibody titre  $\geq 1:10$  at Year 3, Year 4 prior to the booster dose, 7 days post-booster dose, and 28 days post-booster dose. GMTs of anti-JE neutralizing antibody will be calculated.

Evaluation of long-term anti-JE antibody response three and four years after CD-JEV vaccination among children who received the single dose of vaccine will be made at Year 3 and Year 4 prior to the booster dose in terms of JE seroprotection rates. Additionally, the analysis will stratified by the seroprotection status of participants on Day 28 post primary immunization in the previous JEV05 study.

To further describe the antibody response to a booster dose, anti-JE IgM will be measured prior to the booster dose and 7 days post booster dose. Seropositivity will be defined per ELISA manufacturer's instructions.

#### **5.2. Safety variables**

The safety profile will be evaluated in terms of frequency counts and percentage of participants experiencing the following:

- Immediate reactions occurring within 30 minutes after vaccination as observed by study staff.
- Solicited signs and symptoms occurring greater than 30 minutes after receipt of CD-JEV through 7 days post vaccination as observed by study staff or reported by the participants to study staff.
- All other adverse events occurring within one month of CD-JEV receipt as observed by study staff or reported by the participant's parents to study staff.
- SAEs occurring within 28 days of CD-JEV receipt.

### **6. DATA ANALYSIS**

A Statistical Analysis Plan will be specified prior to the first participant first visit and finalized before locking of the database.

#### **6.1. Immunogenicity**

Long-term assessment of the immune response to CD-JEV will be evaluated in terms of percentage of participants with JE neutralizing antibody titre  $\geq 1:10$  at Year 3 and Year 4, just prior to the booster dose. Additionally, the analysis will be stratified by the seroprotection status of participants on Day 28 post primary immunization in previous JEV05 study.

Percentage of participants achieving seroprotection against JE along with 95% confidence interval (CI) will be calculated by group. The method for calculating the 95% CI will be based on the Wilson score method without continuity correction. In addition, the difference in JE seroprotection rates between Groups A and B will be

calculated along with the 95% CI of the difference using the Newcombe-Wilson method without continuity correction.

Similarly, the immune response to the booster dose following a booster dose of CD-JEV given at Year 4 will be assessed in terms of percentage of participants with JE neutralizing antibody titre  $\geq 1:10$  at 7 days post booster dose and 28 days post booster dose. Percentage of participants achieving seroprotection against JE along with 95% CI will be calculated using the Wilson score method without continuity correction.

In addition, GMTs of the anti-JE neutralizing antibody responses and their associated 95% CI will be calculated at Year 3, at Year 4 prior to the booster dose, and at 7 and 28 days post booster dose using the t-test. The GMTs will be compared between Group A and Group B in terms of ratio of the GMTs using the t-test and 95% CI of ratio of GMTs will be calculated.

The GMTs at 7 and 28 days post booster dose will be further compared to the GMTs at Year 4 prior to the booster dose using a paired t-test to evaluate the magnitude of increase in GMTs by group.

Furthermore as part of exploratory analyses to differentiate between a primary or secondary immune response, the immune response to the booster dose will be assessed in terms of the percentage of participants with demonstrated seropositivity for anti-JE IgM prior to the booster dose and 7 days post booster dose. Percentage of participants with seropositivity against JE along with 95% CI will be calculated using the Wilson score method without continuity correction.

